8.2.1 Anticipated Adverse Effects

The following adverse effects could occur in association with insertion, removal, and/or use of the Senseonics CGM System Sensor and/or Transmitter:

- Infection, local or systemic, possibly resulting in sensor removal
- Excessive bleeding during insertion or removal
- Bruising or swelling
- Poor wound healing after insertion or removal
- Keloid and/or scar formation
- Excessive or prolonged pain or discomfort at the Sensor site
- Nerve damage causing tingling, numbness, pain or weakness
- Uncomfortable heating
- Burn
- Electrostatic shock
- Skin irritation and/or redness
- Itch
- Discoloration of skin
- Hematoma formation
- Device migration
- Skin erosion
- Allergic reaction to the device components, local anesthetic, or other medication or materials used in the procedure
- Anxiety and/or nervousness and/or lack of sleep
- Device fragments or particulate matter remaining in the body
- Failure to retrieve device or device left behind
- Difficulty in removing device that may require surgery
- Device malfunctions of the Sensor and/or Transmitter with possible need to remove and/or replace the Sensor and/or Transmitter
- Burning sensation or pain.
- Elevated blood pressure
- Water retention in the tissue, swelling or edema
- Airway spasms

- Shortness of breath
- Circulatory disorders
- Confusion
- Disorientation
- Increased or decreased sensitivity to touch or pain
- Metallic taste
- Sleepiness
- Visual disturbances and/or blurred vision
- Tinnitus
- It is possible that the local anesthetic could cause a reaction other than listed or previously seen.
- Fluid/electrolyte disturbances such as fluid retention
- Muscle weakness
- Osteoporosis
- Peptic ulcer
- Pancreatitis
- Ulcerative esophagitis
- Impaired wound healing
- Headache
- Psychic disturbances and mood swings
- Convulsions
- Glaucoma
- Weight gain
- Nausea and/or vomiting
- Malaise
- Irritability
- Insomnia
- Heartburn
- Hyperglycemia
- Ketosis
- Headaches
- Dizziness, lightheadedness, and/or fainting
- It is possible that the use of the Senseonics CGM system could cause a reaction other than listed or previously seen.
- It has not been determined whether the risks usually associated with injectable dexamethasone apply to the use of dexamethasone elution ring, a highly localized, controlled-release device.
- The dexamethasone ring could cause other adverse events not listed or previously seen.

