8.2.3 Risks Associated with Participation in the Clinical Investigation

This clinical investigation involves subjects with diabetes mellitus. These subjects may experience hyperglycemia and hypoglycemia as a consequence of their existing condition and medical management (e.g. insulin administration). For this study, hyperglycemia and hypoglycemia will not be reported as adverse events unless meeting criteria of a Serious Adverse Event. Episodes of hyperglycemia and hypoglycemia as documented by the Subject SMBG Meter will be reported in an extra listing separate from the AE listings. Should a known side effect(s) occur to administered medication(s) used in the intervention, such effects will be reported as part of the adverse event description and will not be considered a separate adverse event.

The amount of blood drawn for in-clinic testing during the study is below the acceptable limits of blood donation of approximately 475 mL; hence it does not pose any additional unacceptable risk to the subjects.

This clinical investigation involves the following procedures that present risk: placement of an intravenous catheter, frequent blood sampling, and conduct of hyperglycemia and hypoglycemia challenges at the clinic visits. In addition, Subjects in this study may use an insulin pump or syringes to administer subcutaneous insulin.

The following risks are potentially associated with such procedures:

- Routine administration of insulin may cause hematoma, redness, swelling and itch at the injection site, skin rash, itch, sweating, gastro-intestinal complaints, edema, difficulty breathing, palpitations and drop in blood pressure, and even death.
- Hypoglycemic symptoms requiring medical intervention which may include seizures, neuroglycopenia, coma and even death (including occurrence during home use)
- Insulin administration leading to hypoglycemia include: cold sweating, cool and pale skin, fatigue, nervousness, shakiness, anxiety, weakness, confusion, feeling of numbness, hunger, impairment of vision, problems with concentration, headache, nausea, palpitations, coma, or death.

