9.1 Adverse Event Definitions

Adverse Event (AE) is defined as any untoward medical occurrence, unintended disease or injury, or untoward clinical signs (including abnormal laboratory findings) in subjects, users or other persons, whether or not related to the investigational medical device.

NOTE 1 This definition includes events related to the investigational medical device or the comparator.

NOTE 2 This definition includes events related to the procedures involved.

NOTE 3 For users or other persons, this definition is restricted to events related to investigational medical devices.

Serious Adverse Event (SAE) is defined as an adverse event that:

- Leads to death;
- Leads to a serious deterioration in the health of the Subject that either:
 - Results in life-threatening illness or injury; or
 - Results in a permanent impairment of a body structure or a body function; or
 - Requires inpatient or prolonged hospitalization; or
 - Results in medical or surgical intervention to prevent life-threatening illness or injury or permanent impairment to a body structure or a body function;
- Led to fetal distress, fetal death or congenital abnormality or birth defect;
- Significant medical event.

NOTE: Planned hospitalization for a pre-existing condition, or a procedure required by the CIP, without serious deterioration in health, is not considered a serious adverse event.

Anticipated adverse events are AEs that have been identified as possible adverse events related to the investigational device or procedure.

Unanticipated adverse device effects (UADEs) are defined as any serious adverse effect on health or safety or any life-threatening problem or death caused by, or associated with, a device, if that effect, problem, or death was not previously identified in nature, severity, or degree of incidence in the investigational plan or application (including a supplementary plan or application), or any other unanticipated serious problem associated with a device that relates to the rights, safety, or welfare of study subjects.

Severity

Mild: Awareness of a sign or symptom that does not interfere with the Subject's usual activity or is transient, resolves without treatment and with no sequelae

Moderate: Interferes with the Subject's usual activity and/or requires symptomatic treatment

Severe: Symptom(s) causing severe discomfort and significant impact on the Subject's usual activities and/or requires treatment

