9.3.2 Pre-existing Medical Conditions

Pre-existing medical conditions or symptoms reported prior to enrollment will not be recorded as an AE. In the event there is a change in the pre-existing medical condition or symptoms due to the device or study-related procedure, than an AE must be recorded.

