6.8 Safety Endpoints

The safety endpoint is the incidence of device-related or insertion/removal procedure-related serious adverse events (SAEs) in the clinic and during home use through 90 days post-insertion.

An Adverse Event is considered 'related' if the relatedness is categorized as 'possibly related', 'or 'related'. The assessment of seriousness and relatedness made by the Medical Monitor will be used for analysis. The numbers of SAEs and the percentage of patients with SAEs will be reported for each SAE type that is observed, identified as device-related, procedure-related or unrelated to the study (Table 3 in APPENDIX 1). The count and proportion of patients experiencing at least one device-related or procedure-related SAE will be presented. No inferential statistical analysis will be performed.

Other safety endpoints include:

- Incidence of insertion/removal procedure or device-related adverse events in the clinic and during home use.
- Incidence of all adverse events in the clinic and during home use.
- Incidence of hospitalizations due to hypoglycemia, hyperglycemia or ketoacidosis occurring during home use.
- Incidence of reported hypoglycemic and hyperglycemic events occurring during home use.

For each of the adverse event (AE or SAE) categories above, the numbers of AEs and the percentage of patients with AEs will be reported for each AE type that is observed and be stratified by the target age enrollment categories (Tables 4A-4E in APPENDIX 1). A listing (Table 5 in APPENDIX 1) will be prepared that identifies each patient with a reported AE or SAE, and relevant information including date of onset, severity level, seriousness, relatedness to the device or procedure, classification as anticipated or unanticipated, corrective action(s) taken, and resolution status (resolved or ongoing).

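### Protocol 8.2.3 bars all non-serious hyper- and hypoglycemia from AE reporting whatever the cause, which contradicts 9.3.2 and is broader than 9.3.3, so device-related hyperglycemia can drop out of the AE rows

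*SAP*

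**What the plan says.** Protocol 8.2.1 opens its list with "The following adverse effects could occur in association with insertion, removal, and/or use of the Senseonics CGM System Sensor and/or Transmitter". Hyperglycemia is one of the bullets. The same section adds: "It has not been determined whether the risks usually associated with injectable dexamethasone apply to the use of dexamethasone elution ring". Protocol 9.1 gives such a list its meaning: "Anticipated adverse events are AEs that have been identified as possible adverse events related to the investigational device or procedure".

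Three sections then decide whether a glycemic event becomes an AE.

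- Protocol 8.2.3: "hyperglycemia and hypoglycemia will not be reported as adverse events unless meeting criteria of a Serious Adverse Event". Episodes documented by the subject's meter "will be reported in an extra listing separate from the AE listings".
- Protocol 9.3.2: where there is "a change in the pre-existing medical condition or symptoms due to the device or study-related procedure, than an AE must be recorded". Seriousness is not a condition.
- Protocol 9.3.3: the exemption covers mild, clinically non-significant symptoms or glucose values outside the normal range, again unless serious.

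SAP 6.8 lists among the other safety endpoints "Incidence of insertion/removal procedure or device-related adverse events in the clinic and during home use", then all AEs, and later "Incidence of reported hypoglycemic and hyperglycemic events occurring during home use". It tabulates all of them as AE categories. SAP 4.2.2.1 says that meter downloads are used to document hypo- and hyperglycemic episodes.

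**The concern.** Protocol 2.2 makes the incidence of all device- or procedure-related AEs a stated safety objective. The sensor elutes a steroid, and the sponsor lists hyperglycemia as a possible effect of the System. A rule that keeps every non-serious case off the AE form also keeps it away from the investigator's causality and severity grading and from the Medical Monitor's adjudication (protocol 13.13), on which SAP 6.8 relies for relatedness. Glucose values can be recovered from the meter later. A relatedness judgement made at the time cannot.

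Because another section requires the same event to be recorded, sites could in good faith do different things. The two AE rows would then partly reflect which section each site followed.

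**Working it through.** The plan gives no figure for this point, so the check is mainly a reading of the three rules side by side. Every subject has had diabetes for at least a year (inclusion criterion 2), so the pre-existing condition in 9.3.2 is present in all of them.

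| Glycemic event | 8.2.3 | 9.3.2 | 9.3.3 |
|---|---|---|---|
| Serious | reportable | AE if device- or procedure-caused | reportable |
| Non-serious, symptoms more than mild, device- or procedure-caused | not an AE | AE required | outside the exemption |
| Non-serious, mild symptoms or value only, device- or procedure-caused | not an AE | AE required, if it counts as a change in the condition or its symptoms | not an AE |
| Non-serious, symptoms more than mild, not so caused | not an AE | silent | outside the exemption |
| Non-serious, mild symptoms or value only, not so caused | not an AE | silent | not an AE |

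The sections agree on the first and last rows. In the second, 8.2.3 stands against both others; in the third, 8.2.3 and 9.3.3 stand against 9.3.2; in the fourth, 8.2.3 and 9.3.3 differ in scope. The grades in 9.1 are separate from seriousness, so a moderate or severe event that is not serious is possible and the second and fourth rows are not empty by definition.

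Scale, for orientation only:

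- Subjects inserted: 36 (protocol 3.3.1, SAP 3). All carry at least one eluting sensor.
- One-sensor subset: 6 to 9, so two-sensor subjects number 36 − 9 = 27 to 36 − 6 = 30, which is 75.0% to 83.3%. Sensors: 36 + 27 = 63 to 36 + 30 = 66.
- One affected subject moves the device-related AE percentage by 1/36 = 2.8 points, provided that subject has no other device-related AE.
- The documents give no rate. Assuming 0 to 4 affected subjects, the shift is 0 to 4/36 = 11.1 points.
- If every such event were recordable, 0 of 36 would give a one-sided 95% upper bound of 1 − 0.05^(1/36) = 8.0%. Under 8.2.3 a zero for non-serious hyperglycemia follows from the rule and bounds nothing. The plan itself specifies no inference; this figure only shows what a recorded zero would be worth.

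**The case against.** The best defense is that Section 9 governs AE reporting, while 8.2.3 is a risk narrative whose exemption follows a remark about hyper- and hypoglycemia arising from existing diabetes and its management. On that reading 9.3.2 is the specific rule and prevails. This is reasonable as to intent, but the 8.2.3 sentence is written as a study-wide reporting rule and carries no limit by cause. Giving Section 9 priority does not settle everything either, because 9.3.3 has no exception for cause.

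Second, the mention of out-of-range values in 9.3.3 can be read as not confined to mild events. That stands, and it narrows the difference between 8.2.3 and 9.3.3 to symptomatic events that are more than mild. The conflict with 9.3.2 remains.

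Third, the steroid question is followed by other means: dexamethasone levels at Visits 1 to 8, HbA1c at Visits 1, 6, 7 and 8, and meter downloads. These supply exposure and glycemic data, but no relatedness or severity judgement on an event.

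Fourth, the EDC user guideline and the Safety Management Plan are not among the documents reviewed and may set a working rule. That is possible, though it would leave the protocol text contradictory.

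A reader might also infer that non-serious hyperglycemia cannot appear in the home glycemic row. The documents do not support that: 8.2.3 and SAP 4.2.2.1 both point to the subject's meter as the record of episodes. The absence of a glucose cut-off for a reported event is missing detail and does not make a finding by itself. Nor do the documents attribute hyperglycemia to the steroid; the 8.2.1 list pools insertion, removal and use, and says the dexamethasone question is open. Ketosis is on the same list, but neither 8.2.3 nor 9.3.3 exempts it.

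**Conclusion.** The point holds as a contradiction between protocol sections. A non-serious hyperglycemia judged related to the device or a study procedure must be recorded under 9.3.2 and must not be under 8.2.3. For symptomatic events that are more than mild, 8.2.3 also exempts more than 9.3.3 does. The effect falls on two descriptive rows of SAP 6.8, device-related AEs and all AEs, and on the grading behind them. The related-SAE endpoint and MARD are untouched, and the meter listing still captures the readings.

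The size is unknown and may be zero. It depends on how many such events occur and on which section sites follow, and the documents give neither. The 0-to-4-subject range is an assumption used only for illustration. Correction is worthwhile because it is cheap and concerns an effect the sponsor itself anticipates.

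**What to change.** Use the same sentence in protocol 8.2.3 and 9.3.3:

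> Hypoglycemia and hyperglycemia are not reported as AEs unless the event meets an SAE criterion, or is judged possibly related or related to the device, the insertion/removal procedure or another study-related procedure (9.3.2); glucose excursions intentionally induced within the limits of a protocol challenge are exempt unless they are clinically significant (for example, they meet a 7.2.2 stopping criterion).

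This includes other study procedures, as 9.3.2 does, and stops planned challenges from generating AE forms. It resolves unrelated, non-serious events that are more than mild in the direction of 8.2.3: they stay off the AE form, and their readings remain in the meter listing.

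In SAP 6.8, state that the home glycemic row is drawn from the meter data named in SAP 4.2.2.1 and is kept separate from the AE rows.

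The cost is a protocol amendment with sponsor, IRB and regulatory approval (13.4), a short retraining note to sites, a short SAP edit and some extra AE forms. No new procedures or samples are needed. If subjects are already in follow-up, one look back through site notes and meter downloads would cover earlier events.

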6.9 Effectiveness Endpoint

Summary

The effectiveness endpoint will be the mean absolute relative difference (MARD), calculated for all paired Sensor and reference measurements through 90 days post-insertion. For the planned interim analysis, MARD will be based on the first 30 days post-insertion data.

6.9.1.1 Effectiveness Endpoint: Criteria

The effectiveness objective is to descriptively document the distribution of absolute relative difference across all evaluable subjects and to estimate the MARD. The MARD will be estimated initially when all the subjects complete 30 days of Sensor use for the interim analysis, followed by the MARD based on all the follow-up data through 90 days of Sensor use. Descriptive statistics will be provided for the MARD. There is no hypothesis to be tested. No inferential statistical analysis will be performed.

The effectiveness endpoint is the mean absolute relative difference (MARD), defined as the average of absolute difference of paired Senseonics CGM System and reference glucose readings divided by the reference glucose reading (reference) for all reference glucose values, that is:

$$\text{MARD} = \left(\left(\sum \frac{|(\text{Glucose})_{\text{SENSOR}} - (\text{Glucose})_{\text{REFERENCE}}|}{(\text{Glucose})_{\text{REFERENCE}}} \right) / n \right) \times 100\%,$$

Where, n is the total number of CGM and reference glucose pairs during the evaluation period, that is, after 30 days of Sensor use for the interim analysis, and after 90 days of use for the final analysis.

6.10 Exploratory Effectiveness Endpoint

Exploratory effectiveness measures are discussed in this section. Only descriptive statistics will be provided for these exploratory outcomes. All analyses will be provided as described below and by clinic visit day. SMBG glucose values may also be used as reference for some of these analyses.

6.10.1.2 System agreement with reference

The Agreement of the CGM System to reference measurements will be assessed by looking at proportions of all differences $\{ (\text{Glucose})_{\text{SENSOR}} - (\text{Glucose})_{\text{REFERENCE}} \}$ in intervals of $[0 - 20\%]$,

[0-30%], and [0-40%). For readings less than or equal to 80 mg/dL, the absolute difference in mg/dL between the two glucose results will be calculated. For values greater than 80 mg/dL, the absolute percent difference (%) from the reference values will be calculated.

6.10.1.3 Effectiveness measures in full glucose range and different glycemic regions

Mean/median absolute relative difference, mean/median relative difference, mean/median absolute difference when reference YSI≤80 mg/dl, and Agreement between CGM and YSI glucose will be stratified based on YSI glucose ranges. Similar stratification based on CGM glucose will also be performed. (Tables 6A-6F in APPENDIX 1).

6.10.1.4 Concurrence of System Readings and YSI values

Tables for concurrence of system and YSI values will be tabulated (Tables 7A and 7B in APPENDIX 1).

6.10.1.5 Stability of the system throughout sensor life

For the full 90 day duration of the study, performance of the system overtime will be assessed by visit number (Table 8 in APPENDIX 1).

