4 STUDY METHODS, PROCEDURES AND CLINIC VISITS

Each visit is described in detail in this section.

Visit Number	1	2	3	4	5	6	7	8	9
Visit Type	Screening	Sensor Insertion and Training	Accuracy Visit	Accuracy Visit	Accuracy Visit	Accuracy Visit	Accuracy Visit	Accuracy Visit and Sensor Removal	Follow-up Sensor Site Assessment
Study Day and Window		Day 0 (+0 to 30 Days after Visit 1)	Day 1 (\pm 1 Day)	Day 7 (\pm 1 Days)	Day 14 (\pm 1 Days)	Day 30 (\pm 7 Days)	Day 60 (\pm 7 Days)	Day 90 (-3/+7 days)	10 Days Following Sensor Removal (-3/+7 days)
Anticipated Length of Visit	2 Hours	2 to 6 Hours	19 Hours	18 Hours	18 Hours	14 hours	14 hours	15 hours	30 Minutes
Informed Consent Process	X								
Screening history, exam, labs to assess Inclusion/Exclusion	X								
Sensor Insertion		X							

Visit Number	1	2	3	4	5	6	7	8	9
Device Training		X							
Urine pregnancy	X	X	X	X	X	X	X	X	
IV Catheter			X	X	X	X	X	X	
Approximate length of time to collect blood Samples			16 Hours	16 Hours	16 Hours	12.5 Hours	12.5 Hours	12.5 Hours	
Dexamethasone blood draw (4.0 mL) ²	X	X	X ³	X ³	X ³	X	X	X	
HCT	X		X	X	X	X	X	X	
A1C (2.0 mL)	X					X	X	X	
Fingerstick blood glucose and ketones per protocol			X	X	X	X	X	X	
Download Transmitter and BG Meters			X	X	X	X	X	X	
Assess changes in medications and Adverse Events		X	X	X	X	X	X	X	X
Assess Sensor site			X	X	X	X	X	X	X
Hypoglycemia and Hyperglycemia Challenge			X	X	X	X ¹	X ¹	X ¹	
Sleep Assessment				X	X				
Questionnaire								X ⁴	
Sensor Removal								X	
Approximate Samples for glucose analysis			89 (13 hrs @4 per, 3 hrs @ 12 per)	89 (13 hrs @4 per), 3 hrs @ 12 per	89 (13 hrs @4 per), 3 hrs @ 12 per	59 (11.5 hrs @4 per), 1 hr @ 12 per	59 (11.5 hrs @4 per), 1 hr @ 12 per	59 (11.5 hrs @4 per), 1 hr @ 12 per	
Maximum Estimated Blood Draw Volume	6	12	97	97	97	65	65	65	Total=504

1 Only hypoglycemia challenge or hyperglycemia challenge, depending on glucose level

2 Designated subjects will have 3 samples drawn at visit 2. A subset of subjects will have daily blood samples drawn for the first 7 days of sensor wear

for dexamethasone assessment. Remaining subjects may have an additional blood sample drawn during the first 7 days TBD based on the results from the subset.

3 Subjects will have 2 blood samples drawn for dexamethasone assessment, one at the beginning of the visit, and one at the end.

4 Subjects will be asked to complete a questionnaire at the end of sensor wear period.

Visit Details

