4.5.16 Sleep Assessment

Designated subjects will be inserted with two sensors, one in each upper arm. Each subject will spend two overnights in the clinic where they will be instructed to sleep on one side for situations in which compression of the sensor site may occur during sleep. "Sensor drop-out," if a phenomenon of the Senseonics CGM System, will be identified during these periods. Sleep position will not be documented.

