11.1.4 Expected Paired Points by Range*

The expected number of paired YSI/sensor points by YSI glucose range are as follows:

YSI range	Each Day 1, 7, 14 16 Hr. Session	Each Day 30,60,90 12.5 Hr. Session	Total
40-60 mg/dL	166	106	815
61-80 mg/dL	446	285	2194
80-120 mg/dL	1128	722	5550
121-160 mg/dL	1078	690	5303
160-200 mg/dL	712	456	3505
201-250 mg/dL	620	397	3052
251-300 mg/dL	290	186	1426

301-350 mg/dL	127	81	623
350-400 mg/dL	65	42	319
		Total paired points	22786

*Estimates based on 66 sensors. Number of YSI values in each range will be approximately half the number of paired points.

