11.3.2.2 Sample Size and Power Calculation

This study does not feature any inferential statistics. The sample size for the study was not determined based on a power calculation. Instead, the sample size of 36 subjects with sensors inserted was selected based on the objectives of the study and was mutually agreed upon between the Sponsor and the FDA.

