6.10.1.7 Effect of compression on sensor performance during sleep challenges

For the sleep assessment periods during visits 4 & 5, compression may occur to the sensor site when the subject is sleeping at night. The system's difference and agreement with reference and between system precision will be compared between the night time and the day time (Tables 10A and 10B in APPENDIX 1).

6.10.1.8 Mean Absolute Difference between sensor and reference measurements for reference values less than or equal to 80mg/dL

The mean absolute difference (MAD) for reference glucose values less than or equal to 80 mg/dL is defined as the absolute difference of paired Senseonics CGM System and Reference readings for reference glucose values ≤ 80 mg/dL.

$$MAD = \left(\sum |(Glucose)_{SENSOR} - (Glucose)_{REFERENCE}| \right) / n$$

This analysis will quantify both cumulative results as well as stability over time in 30 day intervals (Tables 11A and 11B in APPENDIX 1).

6.10.1.9 Mean Absolute Difference between sensor and reference measurements for system full scale range (40-400mg/dL)

$$MAD = \left(\sum |(Glucose)_{SENSOR} - (Glucose)_{REFERENCE}| \right) / n$$

This analysis will quantify both cumulative results as well as stability over time in 30 day intervals (Tables 11A and 11B in APPENDIX 1).

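### The 90-day stability tables set crude MARD from overnight two-challenge visits (Days 1, 7, 14) beside daytime one-challenge visits (Days 30, 60, 90), so the early-versus-late trend mixes sensor age with session conditions

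*SAP*

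**What the plan says.** **Stability analysis.** SAP 6.10.1.5 says "For the full 90 day duration of the study, performance of the system overtime will be assessed by visit number" and points to Table 8. That shell has one row per visit day (1, 7, 14, 30, 60, 90) with MARD, median ARD and agreement, and no stratum for glucose range or session type. For the measures in SAP 6.10.1.8 to 6.10.1.13, "This analysis will quantify both cumulative results as well as stability over time in 30 day intervals". Tables 11A/11B give MARD on All Results by interval. They have no agreement rows, but they do carry one range-restricted row, mean absolute difference at reference ≤80 mg/dL.

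**Sessions.** Under Protocol 4.4 and 4.5, Visits 3-5 (Days 1, 7, 14) sample from about 18:00 to 10:00, with a 00:00-07:00 overnight block and both challenges for qualifying subjects. On Days 7 and 14 Protocol 4.5.16 adds: "Each subject will spend two overnights in the clinic where they will be instructed to sleep on one side". Under Protocol 4.6, Visits 6-8 (Days 30, 60, 90) sample from about 08:00 to 20:30. The visit table footnote for those visits reads "Only hypoglycemia challenge or hyperglycemia challenge, depending on glucose level". Protocol 5.12.3 assigns the hypoglycemia challenge below 180 mg/dL and the hyperglycemia challenge at or above it.

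**Related outputs already planned.** SAP 6.10 provides every analysis by clinic visit day as well. That covers Tables 6A-6F (by glucose range) and Tables 10A/10B (night against day, Visits 4-5). Table 2.8 in SAP Appendix 2 gives agreement by range within visit, but only for Days 1, 7, 14 and 30, and without MARD.

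**Status.** The section is exploratory and descriptive. For the effectiveness endpoint SAP 6.9.1.1 states: "There is no hypothesis to be tested. No inferential statistical analysis will be performed".

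**The concern.** The session format changes once, between Day 14 and Day 30. Across that boundary sensor age, time of day, deliberate compression and glucose mix all change together. MARD depends on glucose mix wherever relative error differs by range, and on night sampling wherever compression or sleep degrades readings. A difference between early and late rows in Table 8 or Table 11B therefore cannot be read as sensor ageing.

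Table 11B is the most exposed. On the pair counts in Protocol 11.1.4, overnight sessions supply 3×4632/(3×4632 + 2965) = 82% of the Days 1-30 pairs, if all Visit 6 data fall by Day 30. The nominal Day 60 and Day 90 sessions contain no overnight data. At stake is whether a reader of the stability tables can tell a sensor that holds its accuracy from one measured under different conditions late in life.

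**Working it through.** **1. Reproduce the plan's own count.** Protocol 11.1.4 introduces its table with: "The expected number of paired YSI/sensor points by YSI glucose range are as follows". The columns sum to 4632 (16 h session) and 2965 (12.5 h session). 3×4632 + 3×2965 = 22791, against 22786 stated; the gap is rounding.

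**2. Compare its glucose mix between session types.** The daytime/overnight ratio is 106/166 = 0.639, 285/446 = 0.639, ..., 42/65 = 0.646. Every range lies between 0.638 and 0.646. The share at ≤80 mg/dL is 612/4632 = 13.2% overnight and 391/2965 = 13.2% by day. With the ARDs assumed in step 4, that table gives a MARD of 11.24% in both session types, a shift below 0.01 point. It therefore assumes the same mix despite different challenge schedules.

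**3. Mix implied by the challenge targets, per qualifying subject.** Inputs are 25 points <75 mg/dL and 13 points >325 mg/dL per challenge (Protocol 5.12), and 89 samples at Visits 3-5 and 59 at Visits 6-8 (visit table).
- Overnight, both challenges: 25 low, 13 high, 51 middle. Low 25/89 = 28%, high 13/89 = 15%.
- Daytime, hyperglycemia option: 13 high + 11.5 h × 4 = 46 middle, total 59. No induced lows; high 13/59 = 22%.
- Daytime, hypoglycemia option: 25 low + 10.5 h × 4 = 42 middle, total 67. Low 25/67 = 37%. The visit table plans 59 for either option; the extra 8 come from two hours at 5-minute sampling instead of one.

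**4. Crude MARD with no true drift.** MARD = Σ(points × stratum ARD)/Σ(points). Assumed ARDs are 20% low, 10% middle, 8% high; p is the share of daytime challenges that are hypoglycemic.
- Overnight: (25×20 + 51×10 + 13×8)/89 = 1114/89 = 12.5%.
- Daytime, p = 0: (46×10 + 13×8)/59 = 564/59 = 9.6%.
- Daytime, p = 0.5: (564 + 920)/(59 + 67) = 11.8%.
- Daytime, p = 1: (25×20 + 42×10)/67 = 920/67 = 13.7%.
- Break-even: (564 + 356p)/(59 + 8p) = 1114/89 gives p = 0.68.

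**5. Sensitivity to the assumed low-range ARD** (middle 10%, high 8%; shifts are daytime minus overnight, in points):

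| Low ARD | Overnight | p = 0 | p = 0.5 | p = 1 | Break-even p |
|---|---|---|---|---|---|
| 12% | 10.3% | −0.7 | −0.1 | +0.5 | 0.57 |
| 15% | 11.1% | −1.6 | −0.3 | +0.8 | 0.65 |
| 20% | 12.5% | −3.0 | −0.7 | +1.2 | 0.68 |
| 25% | 13.9% | −4.4 | −1.2 | +1.7 | 0.70 |

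Holding the hypoglycemia option at 59 samples, as in the visit table, the 20/10/8 case gives 840/59 = 14.2% at p = 1 and a break-even near 0.63.

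**6. Night component.** 7 h × 4 = 28 of 89 samples (31%) fall in 00:00-07:00. An assumed night excess of 3 points adds 28/89 × 3 = 0.9 point to an affected overnight visit; excesses of 2 to 5 points add 0.6 to 1.6.

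**7. Within the daytime visits.** The challenge is chosen afresh each time. In the 20/10/8 case, p = 0.3 at one visit and 0.7 at another gives 10.9% and 12.6% with no drift.

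**The case against.** The strongest reply is that most of the needed information is already planned. By visit day, Table 6A gives range-specific results on all six days and Table 10A separates night from day at Visits 4-5, the two visits with the compression assessment. Tables 11A/11B track the ≤80 mg/dL range. Days 30, 60 and 90 share one format, so late drift can be compared within a session type. The analysis is descriptive, with no stability criterion to fail. The magnitudes rest on assumed ARDs and on every subject meeting both targets, whereas Protocol 11.1.4 expects only 13.2% of pairs at ≤80 mg/dL, and Protocol 5.12.1 and the observation-subject sections leave some subjects free-range.

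Much of this stands, and it rules out several stronger readings.
- A reader might infer that nothing in the plan separates night from day or stratifies by glucose. That is not so. What remains is that none of these outputs enters the Table 8 trend and Visit 3's night is not split. Table 6A switches to mg/dL at ≤80, and Table 6E gives percent MARD only in three broad ranges with night pairs left in. The by-range shells in Table 2.8 stop at Day 30.
- A reader might infer that the design hides loss of accuracy. The direction is not established: the mix effect reverses above the break-even share, and the documents give no split.
- A reader might infer that a true one-point loss would look like an improvement. With a 3-point night excess on Days 7 and 14 and p = 0.5, that holds against Days 7/14 (13.5% to 12.8%) but not from Day 1 to Day 90 (12.5% to 12.8%).
- A reader might take the uniform scaling in Protocol 11.1.4 as proof that the change of format was overlooked. It shows an inconsistency, not a reason for it.

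**Conclusion.** The concern holds in limited form. The crude early-versus-late contrast in Table 8 and in the All Results MARD rows of Tables 11A/11B is confounded with night sampling and glucose mix, and drift may be hidden or exaggerated. In the 20/10/8 illustration the artefact from mix alone runs from −3.0 to +1.2 points, and an assumed 3-point night excess adds about 0.9 point to the affected overnight visits.

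These figures illustrate possible size; they are not estimates. The documents give no range-specific ARD, night excess or challenge split. The calculation also assumes that all subjects meet the targets and that lows and highs arise only in challenges, so free-range subjects would shrink it. The Day 30 to Day 90 comparison is free of the format change but still depends on which challenge each subject received.

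Because the analysis is exploratory, this does not threaten the endpoint definition. It limits what the stability tables can show, and it can be remedied with data already being collected.

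**What to change.** 1. **SAP 6.10.1.5 and Tables 8, 11A, 11B.** Add to Table 8 (MARD and agreement) and to the MARD rows of Tables 11A/11B a row that omits 00:00-07:00 pairs at Visits 3-5 and weights YSI-range-specific results to one fixed distribution, pooled over all visits, with sparse ranges merged. Compute percent ARD in every range for this row, including ≤80 mg/dL.
2. **Interpretation.** State that the early-versus-late trend is read from the added rows, that Day 30 v 60 v 90 is reported as the same-session-type comparison, and that the crude rows stay as description.
3. **Stated limits.** Say that differences remain after this. Outside the night block the early visits cover 18:00-00:00 and 07:00-10:00 against 08:00-20:30 later, and Day 1 falls in initialization calibration.
4. **Table 2.8.** Extend the shells to Days 60 and 90.
5. **Protocol 11.1.4.** Reconcile the expected pairs, now scaled by about 0.64 in every range, with the different challenge schedules of the two session types.

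The cost is SAP wording and a few table rows, with no new visits or samples. The added rows use about 31% fewer Visit 3-5 pairs (28/89) and are less precise in sparse ranges; for example, Protocol 11.1.4 expects only 42 pairs at 350-400 mg/dL per daytime visit.
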